## 12.6. Appendix 6: Cardiovascular Screening Questions

At screening each subject should be asked the following:

Unrelated to the symptoms you experience with your asthma:

- 1) Do you have any pain or discomfort (such as pressure) in your chest?**
  - If yes, does this pain/discomfort/pressure go to other areas of your body such as neck, jaw, throat, or down your arms (including a numbness feeling in your arm) when it occurs?
- 2) When you walk at an ordinary pace on a level surface does this produce chest pain?** If yes, respond to a and b:
  - a) Does this chest pain or discomfort occur when you are not doing any activities such as resting in bed or sitting in a chair?
  - b) Has this chest pain/discomfort been more frequent or more intense or last longer or come on with less exertion lately?
- 3) When you walk uphill or hurry does this produce chest pain/discomfort?**
- 4) Do you use or have you been previously prescribed nitroglycerine to relieve the discomfort?**
  - If yes, have you needed to increase the number of pills or frequency of using the pills recently?

**If the subject responds “yes” to any of the above questions a study physician should further assess for the presence of undiagnosed or unrecognized angina when evaluating Exclusion Criterion 5 (see Exclusion Criteria Section 5.2 ).**

## 12.7. Appendix 7: Definition of and Procedures for Recording, Evaluating, Follow-Up and Reporting of Adverse Events

### 12.7.1. Definition of Adverse Events

Adverse Event Definition:

- An AE is any untoward medical occurrence in a patient or clinical investigation subject, temporally associated with the use of a medicinal product, whether or not considered related to the medicinal product.
- NOTE: An AE can therefore be any unfavorable and unintended sign (including an abnormal laboratory finding), symptom, or disease (new or exacerbated) temporally associated with the use of a medicinal product.

Events meeting AE definition include:

- Any abnormal laboratory test results (hematology, clinical chemistry, or urinalysis) or other safety assessments (e.g., ECGs, radiological scans, vital signs measurements), including those that worsen from baseline, and felt to be clinically significant in the medical and scientific judgement of the investigator.
- Exacerbation of a chronic or intermittent pre-existing condition including either an increase in frequency and/or intensity of the condition.
- New conditions detected or diagnosed after study treatment administration even though it may have been present prior to the start of the study.
- Signs, symptoms, or the clinical sequelae of a suspected interaction.
- Signs, symptoms, or the clinical sequelae of a suspected overdose of either study treatment or a concomitant medication (overdose per se will not be reported as an AE/SAE unless this is an intentional overdose taken with possible suicidal/self-harming intent. This should be reported regardless of sequelae).
- "Lack of efficacy" or "failure of expected pharmacological action" per se will not be reported as an AE or SAE. However, the signs and symptoms and/or clinical sequelae resulting from lack of efficacy will be reported if they fulfil the definition of an AE or SAE.
- The signs and symptoms and/or clinical sequelae resulting from lack of efficacy will be reported if they fulfil the definition of an AE or SAE. Also, "lack of efficacy" or "failure of expected pharmacological action" also constitutes an AE or SAE.

Events NOT meeting definition of an AE include:

- Any clinically significant abnormal laboratory findings or other abnormal safety assessments which are associated with the underlying disease, unless judged by the investigator to be more severe than expected for the subject's condition.
- The disease/disorder being studied or expected progression, signs, or symptoms of the disease/disorder being studied, unless more severe than expected for the subject's condition.
- Medical or surgical procedure (e.g., endoscopy, appendectomy): the condition that leads to the procedure is an AE.
- Situations where an untoward medical occurrence did not occur (social and/or convenience admission to a hospital).
- Anticipated day-to-day fluctuations of pre-existing disease(s) or condition(s) present or detected at the start of the study that do not worsen.

### 12.7.2. Definition of Serious Adverse Events

If an event is not an AE per definition above, then it cannot be an SAE even if serious conditions are met (e.g., hospitalization for signs/symptoms of the disease under study, death due to progression of disease, etc).

Serious Adverse Event (SAE) is defined as any untoward medical occurrence that, at any dose:

a. Results in death

b. Is life-threatening

NOTE:

The term 'life-threatening' in the definition of 'serious' refers to an event in which the subject was at risk of death at the time of the event. It does not refer to an event, which hypothetically might have caused death, if it were more severe.

c. Requires hospitalization or prolongation of existing hospitalization

NOTE:

- In general, hospitalization signifies that the subject has been detained (usually involving at least an overnight stay) at the hospital or emergency ward for observation and/or treatment that would not have been appropriate in the physician's office or out-patient setting. Complications that occur during hospitalization are AEs. If a complication prolongs hospitalization or fulfills any other serious criteria, the event is serious. When in doubt as to whether "hospitalization" occurred or was necessary, the AE should be considered serious.
- Hospitalization for elective treatment of a pre-existing condition that did not worsen

Serious Adverse Event (SAE) is defined as any untoward medical occurrence that, at any dose:
from baseline is not considered an AE.
d. Results in disability/incapacity
NOTE:

• The term disability means a substantial disruption of a person's ability to conduct normal life functions.

• This definition is not intended to include experiences of relatively minor medical significance such as uncomplicated headache, nausea, vomiting, diarrhea, influenza, and accidental trauma (e.g. sprained ankle) which may interfere or prevent everyday life functions but do not constitute a substantial disruption

e. Is a congenital anomaly/birth defect
f. Other situations:


• Medical or scientific judgment should be exercised in deciding whether reporting is appropriate in other situations, such as important medical events that may not be immediately life-threatening or result in death or hospitalization but may jeopardize the subject or may require medical or surgical intervention to prevent one of the other outcomes listed in the above definition. These should also be considered serious.

• Examples of such events are invasive or malignant cancers, intensive treatment in an emergency room or at home for allergic bronchospasm, blood dyscrasias or convulsions that do not result in hospitalization, or development of drug dependency or drug abuse

g. Is associated with liver injury and impaired liver function defined as:

• ALT <math>\geq</math> 3xULN and total bilirubin* <math>\geq</math> 2xULN (>35% direct), or

• ALT <math>\geq</math> 3xULN and INR ** <math>></math> 1.5.

* Serum bilirubin fractionation should be performed if testing is available; if unavailable, measure urinary bilirubin via dipstick. If fractionation is unavailable and ALT $\geq$ 3xULN and total bilirubin $\geq$ 2xULN, then the event is still to be reported as an SAE.
** INR testing not required per protocol and the threshold value does not apply to subjects receiving anticoagulants. If INR measurement is obtained, the value is to be recorded on the SAE form.

• Refer to Appendix 5 for the required liver chemistry follow-up instructions

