	
eosinophil-deficient mice.
 
Direct assessment of the carcinogenic potential of long-term IL-5 blockade in rodent models not technically feasible.
 
An integrated safety analysis of all placebo-controlled multiple dose asthma trials showed similar reports of malignancies across treatment groups including placebo.
 
Malignancies reported to date across the mepolizumab development program are summarized in the IB.
	
Potential risk for rebound eosinophilia with associated clinical consequences.	
Early published data with Schering-Plough anti- IL5 mAb suggested potential for rebound eosinophilia and disease exacerbation when treatment was stopped [Kim, 2004; Gevaert, 2006]; however, no standard definition of rebound was used and criteria for reporting were variable.
 
There have been no verbatim reports of 'rebound' from completed clinical trials of subjects with asthma, atopic dermatitis and eosinophilic esophagitis.
 
Furthermore, the data do not support an exaggerated return of symptoms after cessation of treatment.
	
Daily monitoring of SAEs by medical monitor; regular systematic review of AE/SAE data from ongoing studies by a GSK safety review team
 
Standard safety assessments to be conducted as outlined in protocol.

Study Procedures		
Potential risk for injury with phlebotomy	Risks with phlebotomy include bruising, bleeding, infection, nerve damage.	Procedures to be performed by trained personnel (i.e., study nurse)

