**DIAGNOSTIC ASSESSMENTS AND OTHER CRITERIA**

15. **Investigator opinion:** Omalizumab treatment has provided significant clinical benefit despite experiencing 2 exacerbations in the past 12 months, and potential benefit from a switch to mepolizumab would not outweigh the potential harm after omalizumab withdrawal for the subject.

16. **Previous participation:** Previously participated in any study with mepolizumab and received investigational product (including placebo).

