#### 7.4.1.1. Time period and Frequency for collecting AE and SAE information

- Any SAEs assessed as related to study participation (e.g., protocol-mandated procedures, invasive tests, or change in existing therapy) or related to a GSK product will be recorded from the time a subject consents to participate in the study up to and including any follow-up contact.
- AEs will be collected from the start of Study Treatment until Exit Visit at the time-points specified in the Time and Events Table (Section 7.1).
- Medical occurrences that begin prior to the start of study treatment but after obtaining informed consent may be recorded on the Medical History/Current Medical Conditions section of the CRF.
- All SAEs will be recorded and reported to GSK within 24 hours, as indicated in [Appendix 7](#)
- Investigators are not obligated to actively seek AEs or SAEs in former study subjects. However, if the investigator learns of any SAE, including a death, at any time after a subject has been discharged from the study, and he/she considers the event reasonably related to the study treatment or study participation, the investigator must promptly notify GSK.

NOTE: The method of recording, evaluating and assessing causality of AEs and SAEs plus procedures for completing and transmitting SAE reports to GSK are provided in Section 12.7, [Appendix 7](#).

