#### 12.7.6. Reporting of SAEs to GSK

SAE reporting to GSK via electronic data collection tool

• Primary mechanism for reporting SAEs to GSK will be the electronic data collection tool.

• If the electronic system is unavailable for greater than 24 hours, the site will use the paper SAE data collection tool and fax it to the Medical Monitor or the SAE coordinator.

• Site will enter the serious adverse event data into the electronic system as soon as it becomes available.

• The investigator will be required to confirm review of the SAE causality by ticking the 'reviewed' box at the bottom of the eCRF page within 72 hours of submission of the SAE.

• After the study is completed at a given site, the electronic data collection tool (e.g., InForm system) will be taken off-line to prevent the entry of new data or changes to existing data

• If a site receives a report of a new SAE from a study subject or receives updated data on a previously reported SAE after the electronic data collection tool has been taken off-line, the site can report this information on a paper SAE form or to the Medical Monitor or the SAE coordinator by telephone.

• Contacts for SAE receipt can be found at the beginning of this protocol on the Sponsor/Medical Monitor Contact Information page.

[figure not shown]

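### The rules for recording asthma worsening as an AE or SAE conflict, exacerbation collection in treatment discontinuers contradicts the visit schedule and the SAP, and the paper SAE route can open after the 24-hour deadline

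*Protocol*

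**What the plan says.** **Risk and mitigation.** Protocol 4.6.1, Table 3, has a row headed "Potential risk for rebound eosinophilia with associated clinical consequences". It cites early data on another anti-IL-5 antibody that "suggested potential for rebound eosinophilia and disease exacerbation when treatment was stopped". The first mitigation entry is "Daily monitoring of SAEs by medical monitor; regular systematic review of AE/SAE data from ongoing studies by a GSK safety review team"; the second is standard safety assessments. Separately, exclusion criterion 15 in Section 5.2 concerns subjects for whom the potential benefit of switching "would not outweigh the potential harm after omalizumab withdrawal for the subject".

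**AE and SAE definitions.** Section 12.7.1 includes as an AE "Exacerbation of a chronic or intermittent pre-existing condition including either an increase in frequency and/or intensity of the condition". The same section excludes the disease under study and its expected course or symptoms, unless they are worse than would be anticipated in that subject. It also has two consecutive bullets on lack of efficacy: the first says that it is not in itself an AE or SAE, the second says that it is. Section 12.7.2 says that if an event is not an AE, "it cannot be an SAE even if serious conditions are met (e.g., hospitalization for signs/symptoms of the disease under study", and gives death from disease progression as a further example.

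**Exacerbation records.** Section 7.3.2.4 collects exacerbations from Visit 2 to Week 32, but for subjects who stop treatment or withdraw it stops at about 4 weeks after the last dose.

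**Reporting times.** Section 7.4.1.1: "All SAEs will be recorded and reported to GSK within 24 hours", with a pointer to Appendix 7. Section 12.7.6 of that appendix: "If the electronic system is unavailable for greater than 24 hours, the site will use the paper SAE data collection tool".

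**The concern.** Two of the three mitigations for the rebound risk, the daily SAE monitoring and the AE/SAE data review, depend on asthma worsening being reported as an AE or SAE. Appendix 7 lets an investigator decide that an asthma admission is neither. The event then goes on the exacerbation pages, for which Section 7.3.2.4 sets no reporting deadline, and the medical monitor need not see it within 24 hours. Because the definitions conflict, two sites could classify the same admission differently, and there is no control arm against which to judge the resulting asthma SAE count.

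The exacerbation pages are also the substitute record for such an event, and their collection window is itself inconsistent for subjects who stop mepolizumab but stay in the study. These are the subjects in whom off-drug worsening could be observed. The point bears on the analysis as well: if a site stops collecting at 4 weeks, an empty record up to Week 32 may mean that nothing happened or that nothing was asked.

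**Working it through.** No power or sample-size figure is involved. The check sets the texts side by side and compares times.

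**1. Is an asthma admission an SAE?**

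| Text | Effect on an asthma admission |
|---|---|
| 12.7.1, inclusion list | AE if frequency or intensity of the condition has increased |
| 12.7.1, first lack-of-efficacy bullet | lack of efficacy is not in itself an AE; its signs and sequelae are, if they meet the definition |
| 12.7.1, second lack-of-efficacy bullet | lack of efficacy is an AE or SAE |
| 12.7.1, exclusion list | not an AE if expected for that subject |
| 12.7.2, opening sentence | if not an AE, then not an SAE despite hospitalisation or death |
| 12.7.2, other situations | intensive emergency-room or home treatment of allergic bronchospasm is an example of a serious event |

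Inclusion criterion 9 requires at least two exacerbations treated with systemic corticosteroids in the 12 months before Visit 1. It does not require admissions, so it does not by itself make an admission expected. It does mean that one more exacerbation need not be an increase in frequency. The text leaves the decision to the investigator and supports either answer.

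**2. Until when are exacerbations collected in a treatment discontinuer?**

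- Section 7.3.2.4: last dose + about 4 weeks.
- Section 5.5.1: discontinuers are asked to complete all remaining visits.
- Section 7.1: exacerbation review at every visit, with no exemption for discontinuers.
- SAP Table 5 (8.1.1): on- and off-treatment analyses of clinically significant exacerbations, of those needing an emergency visit or admission, and of those needing admission.
- SAP 8.1.2: all data to Week 32, discontinuers included.
- SAP 10.4.1: an off-treatment phase that, for discontinuers, begins no later than 28 days after the last dose.

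Example, last dose at Week 8: 8 + 4 = Week 12, and 32 − 12 = 20 weeks outside the window in Section 7.3.2.4. The schedule still places exacerbation reviews at Weeks 16, 20, 24 and 28 and at the final visit in that interval. The SAP therefore plans to analyse data that one protocol sentence closes off and other protocol sections keep open.

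**3. The two 24-hour rules.** Section 7.4.1.1 does not say when its clock starts, and Appendix 7 repeats no 24-hour submission deadline. Assume that the clock starts at awareness. Let h be the hours the system has already been down at awareness (negative if the outage begins later). The paper route opens more than 24 − h hours after awareness, or at once if h is 24 or more.

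| h | Paper opens after awareness | Deadline |
|---|---|---|
| 0 | more than 24 − 0 = 24 h | missed |
| −6 | more than 24 + 6 = 30 h | missed if the SAE was not entered before the outage |
| 12 | just after 24 − 12 = 12 h | can be met |
| 24 or more | at once | can be met |

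So the conflict arises when the outage begins at or after awareness, before the SAE is entered, and is still running when the 24 hours end.

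**The case against.** The best case on the other side is that the safety net is wider than the Appendix 7 text suggests. Much of that stands.

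- **Reliance on SAE monitoring alone.** A reader might infer that Table 3 depends only on SAEs. It does not: it also lists AE/SAE data review and standard assessments, and Sections 7.1 and 7.5 give eosinophil counts at every visit from Visit 1. Those counts show the eosinophilia, though not its clinical consequences.
- **Events recorded nowhere.** A reader might infer this for admissions after the 4-week limit. It is too strong. All deaths need a death page within one week (7.4.2.2.2), and the SAP lists all-cause deaths. The worksheet in 7.4.8 records hospital and emergency visits, and concomitant medication and exacerbations are reviewed at each visit. What is missing is an assured exacerbation or SAE record and, for deaths as well as admissions, assured use of the 24-hour route.
- **The exclusion is conditional.** An event worse than anticipated, or an increase in frequency or intensity, remains an AE and can be an SAE. This makes the finding a conflict left to judgement, not a blanket removal.
- **Number affected.** It is tempting to take 15% of 120 = 18 subjects. Section 9.2.1 applies the 15% to withdrawal from the study, not to stopping treatment while staying in it.
- **Likelihood and timing of rebound.** Table 3 also reports no verbatim cases of rebound in completed asthma trials and no support for an exaggerated return of symptoms. The documents give no time course, so no claim can be made about when rebound would appear.
- **Omalizumab withdrawal is a different harm.** In subjects who stay on mepolizumab, exacerbations are collected to Week 32, beyond the 4.5-month omalizumab wash-out (4.5 × 52/12 = 19.5 weeks). The collection gap concerns those who stop mepolizumab.

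None of this removes the textual conflicts.

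**Conclusion.** Three defects of wording hold.

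1. Sections 12.7.1 and 12.7.2 conflict on whether asthma worsening is an AE. An admission judged expected can miss the route that Table 3 names first, and classification can differ by site.
2. Section 7.3.2.4 contradicts Sections 5.5.1 and 7.1 and the SAP. For a subject who stops after the Week 8 dose and stays in the study, Weeks 12 to 32 have no assured exacerbation record. The documents do not give the expected number of such subjects, so the total effect cannot be sized.
3. The paper trigger can make the 24-hour deadline unattainable, but only for outages of the kind identified above, and only if the clock runs from awareness, which is an assumption. No outage frequency is given.

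The documents do not show that serious asthma events would go unrecorded altogether, or that Table 3's mitigation fails as a whole. The changes are still worth making, because they are cheap and they concern safety reporting and a secondary endpoint.

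**What to change.** 1. Reconcile 12.7.1 and 12.7.2 with Table 3 so that any asthma exacerbation meeting a seriousness criterion goes through the SAE route, and resolve the two opposing lack-of-efficacy bullets. Do not confine all other exacerbations to the exacerbation page: that would remove events that now qualify as AEs under 12.7.1 or as serious under the other-situations item in 12.7.2.
2. Align 7.3.2.4 with 5.5.1, 7.1 and the SAP, so that exacerbations in treatment discontinuers are collected until their last study visit. The limit of about 4 weeks can remain where SAP 10.4.1 already has it, as part of the on-treatment analysis window.
3. State in 7.4.1.1 when the 24-hour clock starts. In 12.7.6, allow the paper form or telephone whenever electronic entry cannot be completed within 24 hours of awareness.

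The cost is amendment wording and some additional SAE reports for asthma admissions. No new visits or tests are needed.

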### 12.7.3. Definition of Cardiovascular Events

Cardiovascular Events (CV) Definition:
Investigators will be required to fill out the specific CV event page of the CRF for the following AEs and SAEs: 

• Myocardial infarction/unstable angina

• Congestive heart failure

• Arrhythmias

• Valvulopathy

• Pulmonary hypertension

• Cerebrovascular events/stroke and transient ischemic attack

• Peripheral arterial thromboembolism

• Deep venous thrombosis/pulmonary embolism

• Revascularization

### 12.7.4. Recording of AEs and SAEs

AEs and SAE Recording:

• When an AE/SAE occurs, it is the responsibility of the investigator to review all documentation (e.g., hospital progress notes, laboratory, and diagnostics reports) relative to the event.

• The investigator will then record all relevant information regarding an AE/SAE in the CRF

• It is not acceptable for the investigator to send photocopies of the subject's medical records to GSK in lieu of completion of the GSK, AE/SAE CRF page.

• There may be instances when copies of medical records for certain cases are requested by GSK. In this instance, all subject identifiers, with the exception of the subject number, will be blinded on the copies of the medical records prior to submission of to GSK.

• The investigator will attempt to establish a diagnosis of the event based on signs, symptoms, and/or other clinical information. In such cases, the diagnosis will be documented as the AE/SAE and not the individual signs/symptoms.

